9 STATISTICAL CONSIDERATIONS

9.1 STATISTICAL HYPOTHESES

Primary Efficacy Endpoint(s):

- H1 (Objective 1): There will be an improvement in the oral hygiene clinical outcomes (lower plaque index and lower gingival index) from baseline to Month 3 and Month 6, and from Month 3 to Month 6. Treatment Group 1 will have a higher rate of improvement than the control group while Treatment Group 2 will have the highest rate of improvement.
- H2b (Objective 2b): The effects of the intervention on oral hygiene clinical outcomes (i.e., plaque index and gingival index) will be mediated by a set of mediating variables controlling for selected key covariates.
- H3a (Objective 3a): The effects of the intervention on oral hygiene clinical outcomes (i.e., plaque index and gingival index) will be mediated by oral hygiene behavioral outcomes controlling for selected key covariates.
- H3b (Objective 3b): The effects of the intervention on oral hygiene clinical outcomes (i.e., plaque index and gingival index) will be mediated by care partner's factors, and then mediated by oral hygiene behavioral outcomes controlling for selected key covariates.

Secondary Efficacy Endpoint(s):

- H1 (Objective 1): There will be an improvement in the oral hygiene behaviors (better oral hygiene skills and higher frequency of toothbrushing) from baseline to Month 3 and Month 6, and from Month 3 to Month 6. Treatment Group 1 will have a higher rate of improvement than the control group while Treatment Group 2 will have the highest rate of improvement.
- H1 (Objective 1): There will be an improvement in the oral hygiene behaviors (longer duration of toothbrushing) from the first week of the intervention (average in Week 1) to Month 3 (average in Month 3) and Month 6 (average in Month 6), and from Month 3 to Month 6. Treatment Group 2 will have longer duration of toothbrushing than the Treatment Group 1.
- H2a (Objective 2a): The effects of the intervention on oral hygiene behavioral outcomes (i.e., the duration and frequency of toothbrushing and oral hygiene skills) will be mediated by a set of mediating variables controlling for selected key covariates.

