9.2 SAMPLE SIZE DETERMINATION

Since we will collect data from the predictors [X], mediators [M] and outcomes [Y] at all three time points (baseline, 3 months, 6 months), we will use generalized linear mixed models to account for longitudinal repeated measurements over time to produce sample based inferential effects, which is a group-specific averaged effect size slope over all three time points to estimate each pathway strength.

For the power analyses, we proposed a small to medium effect size of 0.3 for our main outcome analyses without mediators. This was based on a combination of the effect size that is needed to detect what is reasonably thought to be a meaningful change and guidance from our pilot study. Thus, for the main effect we need a minimum of 107 subjects to reach 80% power at a significance level of 0.05. For the sequential mediation models, a sample of 120 provided at least 85% power at a significance level of 0.05. Thus, our target is to have a sample size of 120 to complete the intervention. However, if our attrition rate is higher than originally predicted, the sample size will be increased up to 150.

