*Target accrual: 120 dyads

Study Design

This is a three parallel arm randomized controlled trial (RCT) to evaluate the effectiveness of a care partner-assisted intervention to improve oral hygiene in individuals (≥ 60 years) with mild dementia. Participant-care-partner dyads were randomized into 1 of 3 groups: Treatment Group 1 (**TG1**), Treatment Group 2 (**TG2**), and the Control Group (**CG**) stratified by site. **TG1** and **TG2** were given smart electronic toothbrushes. Only **TG2** will receive in-home and telephone coaching throughout the duration of the study and were instructed to record daily brushing habits. The coaching sessions included individualized instruction on oral hygiene technique, cueing strategy development, or oral hygiene monitoring and coaching. **TG1** and **CG** did not receive coaching sessions. While randomization occurred at the dyad level (participant-care partner), primary study outcomes will be assessed at the participant level. The study duration was 6 months, including a 3 month intervention phase, in which coaching and educational modules were delivered, followed by a 3 month maintenance phase in which no coaching or educational modules were presented to participants. Data was collected by the study team at three visits: baseline, 3-months (end of active intervention phase), and 6-months (end of three-month maintenance phase). The primary endpoint is oral hygiene (plaque index, gingival index) at 3 months, with a secondary endpoint of 6 months to explore maintenance of intervention effects.

Study Aims

Aim 1: Evaluate the effectiveness of a care partner-assisted intervention to improve oral hygiene and oral hygiene behaviors in individuals with mild dementia.

Hypothesis 1a: Compared to CG, both T1 and T2 will result in improved oral hygiene as measured by reduced plaque index, and reduced gingival index, at 3 months.

Hypothesis 1b: T2 will have higher improvement than T1, relative to CG, in oral hygiene as measured by a greater reduction in plaque index, and gingival index, at 3 months.

Aim 2: Assess changes in mediating factors/process outcomes, including communication between the dyads, oral health knowledge, and self-efficacy for both participants and care partners to understand mechanisms of the intervention.

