Statistical Analyses (Aim 1): To examine between-group differences in baseline characteristics and outcome variables, we will use Chi-square tests or Fisher's exact tests to analyze categorical variables and a one-way analysis of variance (ANOVA) for continuous variables. The effectiveness hypotheses will be analyzed using a linear mixed modeling framework with random effects. Specifically, longitudinal outcomes (e.g. plaque index) will be regressed on a treatment indicator, timepoint indicator, interaction of the two, and additional participant-specific covariates as needed. That is for the i^{th} person and t timepoint, $\text{Plaque}_{it} = \alpha_i + \beta_0 + \beta_1 \cdot \text{Site}_i + \beta_2 \cdot X_i + \beta_g \cdot \text{Group}_i + \beta_t \cdot \text{Time}_t + \beta_{gt} \cdot \text{Group}_i \times \text{Time}_t + \varepsilon_{it}$, where the terms represent the following: α_i person-specific random effects, β_0 overall mean plaque, β_1 site effects, X_i additional participant-specific covariates, β_g group effects, β_t time effects, and β_{gt} the interaction effect between group and time. Covariates determined a priori (including: baseline index scores, baseline functional status) will be included via the flexible X_i term. If data suggest a between-group difference (e.g. significant interaction between time and group) on the primary outcomes of interest, we will conduct the following pairwise comparisons using estimated means (**TG1 vs. CG**; **TG2 vs. CG**), at 3 months and 6 months. To control for multiple comparisons, pairwise comparisons will incorporate a False Discovery Rate-controlling procedure (e.g. Benjamini-Hochberg) which yields the desired type-I error rate of 5%. Lastly, depending on the distribution of the proportions for the primary outcomes (plaque, gingival indices) we may explore alternative distributions (e.g. beta regression) if it improves model fit. To address secondary outcomes including: 1) participants' frequency of toothbrushing, 2) participant's duration of toothbrushing, 3) participants frequency of interdental cleaning, 4) participant's interproximal cleaning technique, and 5) participants' oral hygiene skills score, and 6) participants' oral health knowledge score, we will use the same analytic approach outlined above consisting of linear mixed modeling with random effects. Given the overall sample size and number of secondary outcomes, all secondary outcome analyses will incorporate an appropriate False Discovery Rate-controlling procedure (e.g. Benjamini-Hochberg).

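### The SAP makes 3 months primary, but its 3-month contrasts run only after an all-visit test, have no priority over month 6, and leave out TG2 versus TG1

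*Combined protocol and SAP*

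**What the plan says.** The SAP's Study Design section ranks the visits: "The primary endpoint is oral hygiene (plaque index, gingival index) at 3 months, with a secondary endpoint of 6 months". Under Study Aims, Hypothesis 1a holds that both treatments "will result in improved oral hygiene as measured by reduced plaque index, and reduced gingival index, at 3 months". Hypothesis 1b, that TG2 improves more than TG1, is set at the same visit.

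The SAP's Statistical Analyses (Aim 1) section fits a mixed model with group, time and their interaction, on data from baseline, 3 and 6 months. The follow-up comparisons are conditional: "If data suggest a between-group difference (e.g. significant interaction between time and group) on the primary outcomes of interest, we will conduct" TG1 versus CG and TG2 versus CG. They are made "at 3 months and 6 months. To control for multiple comparisons, pairwise comparisons will incorporate a False Discovery Rate-controlling procedure". No rule puts month 3 ahead of month 6, and TG2 versus TG1 is not listed.

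The protocol differs again. Section 9.1 states the primary hypothesis as improvement ("lower plaque index and lower gingival index) from baseline to Month 3 and Month 6, and from Month 3 to Month 6") and ranks none of the three intervals. Section 9.4.2 takes an interaction with p below 0.05 as evidence of efficacy for TG2 and names no visit. It leaves the details of the primary analysis to the SAP.

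**The concern.** The primary quantity is a difference between arms at month 3. The test that decides whether this difference is examined also draws on month 6, which the SAP calls secondary. Two consequences follow. An effect confined to month 6 can satisfy the entry condition, and under protocol 9.4.2 that alone counts as efficacy. Conversely, a real month-3 effect may never be examined because the joint test spends degrees of freedom on month 6. Months 3 to 6 carry no coaching, so partial fading is plausible. The SAP lists 54 completers against a target of 120 dyads, so power is scarce. Separately, Hypothesis 1b cannot be answered from the two contrasts against control.

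**Working it through.** **The plan's own figure.** Protocol 9.2 asks for at least 107 subjects for 80% power at 0.05 with an effect size of 0.3. If 0.3 is read as Cohen's f for three groups (an assumption; the metric is not stated), noncentrality is N × 0.09 on 2 df. The chi-square approximation gives 79.98% power at 107 and a required N of 108, so the figure reproduces. The exact F gives 78.75% at 107 and a required N of 111. This is an overall group test and is not tied to month 3.

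**Inputs.** Completers are 19 CG, 18 TG1 and 17 TG2 (SAP sample size table), and tests are two-sided at 0.05 (SAP General Approach). The documents give no SD, correlation or month-3 effect. Assumed: SD 1 at each visit, equal correlation ρ = 0.5 between visits, effects of 0 / 0.4 / 0.8 SD, and categorical time, so that the interaction has 4 df.

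**Formulas.** The weighted mean effect is (18 × 0.4 + 17 × 0.8)/54 = 0.385. The between-group sum of squares is SS = 19(0.385)² + 18(0.015)² + 17(0.415)² ≈ 5.75. Let r be the share of the month-3 effect left at month 6. The two changes from baseline have covariance (1−ρ)[[2,1],[1,2]]. Noncentralities are:

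- Unadjusted interaction, 4 and 102 df: SS × 2(1 − r + r²)/[3(1−ρ)]
- Unadjusted change to month 3, 2 and 51 df: SS/[2(1−ρ)]
- Baseline-adjusted month 3, 2 and 50 df: SS/(1−ρ²)
- Baseline-adjusted joint test of months 3 and 6, 4 and 100 df, at ρ = 0.5: SS × (1.5 − r + 1.5r²)

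**Results at ρ = 0.5** (noncentrality, power):

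| Effect | Interaction, unadjusted | Month 3, unadjusted | Joint 3 and 6, adjusted | Month 3, adjusted |
|---|---|---|---|---|
| Fully maintained (r = 1) | 7.66, 56% | 5.75, 54% | 11.50, 76% | 7.66, 67% |
| Half faded (r = 0.5) | 5.75, 43% | 5.75, 54% | 7.90, 58% | 7.66, 67% |

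Like must be compared with like: 43% against 54%, or 58% against 67%. Setting 43% against 67% would mix the choice of visit with the gain from baseline adjustment.

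**How special the half fade is.** The factor 1 − r + r² is smallest at r = 0.5, so this is the worst case for the unadjusted interaction. Its power at 100/75/50/25/0% retention is 56/47/43/47/56%. At r = 0.5 the interaction and the month-3 change have the same noncentrality for any ρ, so the loss there comes entirely from the extra degrees of freedom.

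**Month-6-only effect.** With 0.4 and 0.8 SD at month 6 and nothing at month 3, the interaction's noncentrality is 5.75 × 2/[3 × 0.5] = 7.66, so it is significant in 56% of trials (48% to 67% for ρ 0.4 to 0.6). A month-3 test rejects in 5%. The full SAP sequence was also simulated: 4-df interaction, then Benjamini-Hochberg over four baseline-adjusted contrasts, 5,000 runs per scenario. At ρ = 0.5, 43% of trials end with a significant month-6 contrast and none at month 3, and about 4% with a significant month-3 contrast. Across ρ 0.3 to 0.7, a TG2 effect of 0.5 or 0.8 SD, and TG1 at half or all of it, the false month-3 rate is about 2% to 6%.

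**The case against.** The SAP does plan 3-month contrasts, and Hypothesis 1a would be answered by them, not by the interaction. The 56% is the rate at which the entry condition is met; false 3-month findings stay near or below the nominal level. This stands. A reader might infer that month 3 has no test at all, or that the visits are pooled into one estimate. Neither is so: the interaction is a joint test, followed by visit-specific contrasts.

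The protocol hands the primary-analysis details to the SAP, so 3 months may be a deliberate refinement of 9.1. That also stands, but it does not settle the mismatch inside the SAP between Study Design and the Aim 1 analysis. A reader might also count the averaged slope in protocol 9.2 ("group-specific averaged effect size slope over all three time points") as a further definition of the primary time point. That phrase concerns estimating pathway strength across predictors, mediators and outcomes, and does not define one.

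The 4 df are assumed. The interaction is offered only as an example, and the SAP does not explain how the baseline index can be both a covariate and a repeated outcome. Its reference to a timepoint indicator suggests categorical time. With linear time, the interaction's power for a half fade of the 0.8 SD effect would be lower still, at 13% to 26% for ρ 0.3 to 0.7.

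Finally, a joint test is not always worse. If the effect is fully maintained, the adjusted joint test gains about 9 points over month 3 alone. This stands and is a real cost of the change. That joint test is not, however, the unadjusted interaction, which has 56% in the same case.

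**Conclusion.** The point holds in a limited form. The SAP's entry condition and comparison family do not match its stated primary time point: month-3 contrasts depend on a joint test that the secondary visit can satisfy or weaken, and TG2 versus TG1 is missing. On matched comparisons the loss for a half-fading effect is 11 points unadjusted (54 − 43) or 9 points adjusted (67 − 58), under the assumed effects, correlation and categorical time.

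Two stronger readings are not supported. A reader might infer that a month-6-only effect yields the primary claim. Under the SAP it yields a met entry condition and often a month-6 finding; only under protocol 9.4.2 would the interaction itself count as efficacy. A reader might also infer that any fading effect is diluted. On these assumptions a fully faded effect gives the unadjusted interaction the same 56% as a maintained one. The matter should be corrected, but it does not invalidate the design.

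**What to change.** In the SAP, define the primary test for each index as the month-3 group comparison from the planned mixed model, adjusted for the baseline index and not conditional on the interaction. Take TG1–CG and TG2–CG (Hypothesis 1a) and TG2–TG1 (Hypothesis 1b) at month 3, with multiplicity control within that month-3 family. Report the interaction, the month-6 contrasts and the month 3-to-6 change as secondary. Align protocol 9.1 and 9.4.2 with this. Make the change before outcomes by arm are examined.

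The cost is wording and a few contrasts from a model already planned, with no new data. A month-6-only effect becomes a secondary result. If the effect is fully maintained, power is about 67% where an adjusted joint test would have 76%.

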4.3 JUSTIFICATION FOR INTERVENTION

Mode of intervention delivery: The intervention uses a combination of in-home face-to-face and telephone delivery. Recent meta-analyses demonstrate that both face-to-face and telephone (or other technology) intervention delivery are effective when the caregiver is the focus of the intervention^{29,30} but a combination of approaches was found to be most effective.³¹ A systematic review found face-to-face delivered interventions with caregivers were most effective for skill-building intervention such as ours.³⁰ Because of this evidence and because our intervention includes both the individual with mild dementia and the care partner, we chose to use a combination of face-to-face and telephone contact.

Minimum-acceptable participation in, or exposure to, the intervention in order to have evaluable data.

Three months is the Minimum acceptable length of participation in order to have evaluable data. See section 6.1.2 for dosing determination.

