7.2 PARTICIPANT DISCONTINUATION/WITHDRAWAL FROM THE STUDY

An investigator may discontinue a participant from the study for the following reasons:

1. Any event or medical condition or situation occurs such that continued collection of follow-up study data would not be in the best interest of the participant or care partner or might require an additional treatment that would confound the interpretation of the study
2. The participant no longer meets the inclusion criteria or meets an exclusion criterion (either newly developed or not previously recognized) that precludes further study participation
3. Death of participant or moving away from study site area
4. Lost to follow-up; unable to contact participant

The reason for participant discontinuation or withdrawal from the study will be recorded on the Discontinuation/Withdrawal Case Report Form (CRF). Participants who sign the informed consent form and are randomized but do not receive the study intervention may be replaced. Participants who sign the informed consent form, and are randomized and receive the study intervention, and subsequently withdraw, or are discontinued from the study, will be replaced if the enrollment window is still open.

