General Approach: The overall goal of this study is to demonstrate the effectiveness of the two intervention strategies (TG1, TG2) against that of CG. The primary outcomes are plaque index, which is quantified as the proportion of sites with plaque deposits on at least less than 1/3 of crown, and gingival index, which is quantified as the proportion of sites with at least some mild inflammation. While the unit of randomization is at the dyad level, the primary outcomes will be evaluated at the individual level. As participants and care-partners contribute repeated measures (at baseline, 3 months and 6 months), we will use a linear mixed modeling approach for the analysis of the primary hypotheses, to account for correlation among repeated measures from the same individual. Analyses for all study outcomes will be conducted according to the intention-to-treat (ITT) principle, where all participants are analyzed according to the group in which they were randomized, irrespective of their receipt of allocated treatment. For our primary analysis we will conduct a

complete case analysis, thus excluding participants who are lost to follow up. As a sensitivity analysis, we will use the strategy of last-observation-carried-forward (LOCF) (thus assuming no change), to impute missing values for participants lost to follow up, if a monotone pattern is demonstrated in complete data. A strategy of LOCF is conservative in that it may bias results towards a null effect, but eliminates bias related to differential dropout, especially in the case where participants with no improvement are less likely to complete follow-up assessments. Statistical analyses will be performed in R version 4.4.0. All statistical tests will be two-sided, and a p-value of < 0.05 will be considered statistically significant.

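### As worded, the primary complete-case rule discards observed month-3 primary-endpoint values, and the SAP's claim that LOCF removes differential-dropout bias is false in general

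*Combined protocol and SAP*

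**What the plan says.** The SAP, Study Design, sets the time point: "The primary endpoint is oral hygiene (plaque index, gingival index) at 3 months". Six months is secondary.

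The SAP, General Approach, then makes four statements:

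- Model: "we will use a linear mixed modeling approach for the analysis of the primary hypotheses", with repeated measures at baseline, 3 and 6 months.
- Principle: intention to treat (ITT), under which "all participants are analyzed according to the group in which they were randomized, irrespective of their receipt of allocated treatment".
- Primary handling of missing data: a "complete case analysis, thus excluding participants who are lost to follow up".
- Sensitivity analysis: LOCF, to be run "if a monotone pattern is demonstrated in complete data", with the justification "A strategy of LOCF is conservative in that it may bias results towards a null effect, but eliminates bias related to differential dropout". No other missing-data sensitivity analysis is planned.

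Protocol section 4.3 says: "Three months is the Minimum acceptable length of participation in order to have evaluable data". Section 4.4 counts a participant as a completer only after the 6-month visit and, where applicable, all four coaching modules. Section 7.2 lists "Lost to follow-up; unable to contact participant" among the reasons for which an investigator may discontinue a participant. Section 9.3 defers a per-protocol set to the SAP, and the SAP describes none.

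**The concern.** The complete-case sentence is the only statement of who enters the primary analysis, and it excludes people. Someone assessed at month 3 and lost before month 6 has an observed primary-endpoint value and meets the protocol's own three-month minimum for evaluable data. Followed literally, the rule removes that value because a secondary time point is missing. A mixed model needs no such exclusion.

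Two things are at stake. One is precision, in a trial with 54 completers against a target of 120 dyads. The other is bias in the month-3 contrast, if those who leave after month 3 differ in response from those who stay. The LOCF analysis is meant to reassure on exactly this, but the SAP credits it with a property it does not have and attaches a condition that may prevent it from being run.

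**Working it through.** **1. Counts.** From the table of sample size as of 05/08/24, consented minus completed: Control Group (CG) 20 − 19 = 1; Treatment Group 1 (TG1) 20 − 18 = 2; Treatment Group 2 (TG2) 20 − 17 = 3. Totals are 60 and 54, which reproduces the table. TG2 versus CG (3/20 versus 1/20), Fisher's exact test: p = 0.60. The table does not say when or why the six failed to complete. Some may still have been in follow-up on that date, and a TG2 participant can be a non-completer through a missed coaching module. The number of observed month-3 values at risk is therefore 0 to 6.

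**2. Precision, if all non-completers are excluded.** Let a and c be the TG2 and CG non-completers who left after month 3. The ratio of the month-3 SE under exclusion to the SE with all observed values is

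sqrt[(1/17 + 1/19) / (1/(17+a) + 1/(19+c))].

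- a = 0, c = 0: 1.000.
- a = 3, c = 1: sqrt(0.11146 / 0.10000) = 1.056.
- TG1 versus CG (18 and 19 completers): 1.000 to sqrt(0.10819 / 0.10000) = 1.040.

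**3. Bias when dropout depends on response equally in both arms.** Assumptions, none from the documents: 20 per arm, no true effect, correlation 0.5 between visits, baseline-adjusted month-3 contrast. The dropout score is r × standardised change + sqrt(1 − r²) × noise, and the highest (least improved) scorers are removed. There were 40,000 simulated trials per cell (Monte Carlo SE 0.0015). Entries are the shift in SD; positive favours TG2.

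| Lost after month 3 (TG2/CG) | r = 0.3 | r = 0.5 | r = 1 |
|---|---|---|---|
| 0/1 | −0.022 | −0.037 | −0.077 |
| 1/1 | 0.001 | −0.001 | 0.001 |
| 1/0 | 0.022 | 0.036 | 0.076 |
| 2/1 | 0.017 | 0.034 | 0.065 |
| 2/0 | 0.039 | 0.071 | 0.138 |
| 3/1 | 0.034 | 0.059 | 0.127 |
| 3/0 | 0.061 | 0.097 | 0.201 |

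With r = 0 every shift is within 0.003 of zero. For scale, SE = sqrt[0.75 × (1/17 + 1/19)] = 0.289 SD, where 0.75 = 1 − 0.5². The 3/1 shift at r = 0.5 is 0.059 / 0.289 = 0.20 SE. With visit correlation 0.3 or 0.7 it is 0.062 or 0.056.

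**4. Bias when the link differs by arm.** Same set-up. With 1/1 lost, r = 0.5 in TG2 and 0 in CG, the shift is 0.036 SD towards TG2, although losses are equal. With 3/1 lost, r = 0 in TG2 and 0.5 in CG, it is about 0.04 SD against TG2, the arm that loses more. Only TG2 is coached, so different reasons for leaving are plausible. Counts alone do not fix the direction.

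**5. Does keeping observed visits help?** In a large simulation (500,000 per arm, no true effect, both arms improving 0.5 SD), 15% versus 5% were lost after month 3, depending on the month-3 score. The month-3 contrast was −0.088 SD under complete case and −0.002 SD under likelihood analysis of all observed data.

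**6. The LOCF claim.** Suppose both arms truly change by −0.10, and 3 of 20 in TG2 and 1 of 20 in CG are lost at random before month 3. Carrying baseline forward gives −0.10 × 17/20 = −0.085 in TG2 and −0.10 × 19/20 = −0.095 in CG. Unequal dropout alone creates a difference of 0.010 against TG2. With 0 and 1 lost, the values are −0.100 and −0.095, in favour of TG2.

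The bias need not be towards the null. If both arms worsen by 0.5 SD and 15% versus 5% are lost at random before month 3, LOCF gives about 0.5 × (0.05 − 0.15) = −0.05 SD, a false benefit (simulated −0.052).

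**7. The LOCF condition.** Complete data have no missingness pattern. The condition could refer to monotone missingness or to a monotone outcome trend among completers. Under the first reading, one missed month-3 visit followed by an attended month-6 visit would switch LOCF off. Under the second, the shape of the results would decide.

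**The case against.** The strongest reply is that the sentence means less than it says. The SAP plans a repeated-measures mixed model and contrasts complete case with LOCF imputation, so complete case may only mean that nothing is imputed. On that reading month-3 values stay in and the analysis is sound. This is a fair possibility, and a reader should not conclude that data will certainly be discarded. But the text names participants as the unit excluded and nothing else in the SAP corrects it, so two analysts could build different primary data sets.

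A reader might also infer that complete case breaks the SAP's ITT statement. That goes too far. ITT is defined there as analysis by randomised group regardless of treatment received, not as full retention.

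Nor should section 7.2 be read as a full list of reasons for leaving. It covers what an investigator may do and omits voluntary withdrawal, and the SAP may use lost to follow-up generically. What stands is that the scope of the exclusion is not stated. The precision figures above assume that all non-completers are excluded.

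Finally, the effect is small, and the SAP openly says LOCF may bias towards the null. Both points are right. LOCF also does no harm at month 3 when all loss comes later, because nothing is then imputed at month 3. That does not rescue an unqualified claim that it eliminates the bias.

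**Conclusion.** The point holds as a defect of wording with a modest, conditional effect, and it is worth fixing because the fix is nearly free. Between 0 and 6 observed primary-endpoint values are at stake. If all non-completers are excluded, the TG2 versus CG SE is 0% to 5.6% larger. With random loss, only precision suffers. With 3 versus 1 lost after month 3 and an equal dropout-response correlation of 0.5, the shift is about 0.06 SD, or 0.2 SE. These biases rest on the stated assumptions and are not estimates for this trial.

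Two stronger readings are tempting. The first is that the 3, 2, 1 pattern of non-completion shows differential dropout in favour of the coached arm. It does not: the counts are compatible with chance, timing and reasons are unknown, and the direction of any bias cannot be told in advance. The second is that the false-positive rate is materially inflated. A rough null simulation of the interaction test followed by Benjamini-Hochberg, without the planned covariates, gave a false TG2 versus CG claim at month 3 in 0.2% of trials with no loss, 0.3% with random loss, and 0.6% when the least improved always leave. No such claim is made here.

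The statement that LOCF eliminates differential-dropout bias is false in general, whatever the sizes turn out to be.

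**What to change.** In the SAP's General Approach:

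- Define the primary analysis as the planned mixed model on all randomised, consented participants, as randomised, using every observed visit. State that month-3 values are kept for those who leave later, whatever the reason.
- Move complete case to a sensitivity analysis, and say whether it applies per visit or across visits.
- Delete the claim that LOCF eliminates differential-dropout bias.
- Remove the monotone condition, so that the missing-data sensitivity analysis is always run.
- Report non-completion by arm with timing and reason.

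If exclusion of missing visits only was always intended, the first change simply records it. The cost is a few sentences of SAP wording and slightly more analysis work, with no new data collection.
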